Investigating mechanisms underlying spinal cord stimulation efficacy using virtual reality and full body illusion

IRB Number: 2016H0202

IRB Approval Date: 08/July/2017

Document Date: 08/July/2017

NCT Number: NCT02970006

PI: [name]

Investigating mechanisms underlying spinal cord stimulation efficacy using virtual reality and full body illusion

Abstract

Epidural spinal cord stimulation (SCS) is an approved treatment for truncal and extremity neuropathic pain. The mechanisms underlying the efficacy of SCS are unknown. Recent advances in cognitive neuroprosthetics using virtual reality allow for modulation of body perception and bodily experience, which has also been shown to modulate pain perception. The present research proposal plans to merge expertise in cognitive neuroprosthetics from the laboratory of cognitive neuroscience of [name] with neuromodulation techniques from the Center for Neuromodulation directed by [name], in order to test the analgesic properties of the combination of epidural spinal cord stimulation with a new system of multisensory stimulation based on virtual and enhanced reality (i.e., neuro-visual stimulation). We propose to study this hypothesis prospectively in 25 patients with implanted SCS systems for the treatment of chronic neuropathic pain. Primary outcomes will be pain reduction (based on subjective, functional and physiological measures) and changes in body perception (based on subjective and objective measures). The present study will generate a proof-of-concept for the application of neuro-visual stimulation for the treatment of chronic pain and will form the basis for future NIH funding application.

Study hypothesis

We hypothesize that SCS combined with virtual leg illumination (provided through a wearable headset (OculusRift, OculusVR, Irvine, CA) and a custom-designed virtual reality leg scenario) will lead to controlled analgesia induction, boosting analgesic effects obtained with standard SCS treatments and will further be associated with changes in the perception of the affected body part.

Specific Aims and predictions

1. To quantify pain reduction induced by the combination of SCS and neuro-visual stimulation (using virtual reality) in a significant cohort of patients with implanted SCS for the treatment of chronic neuropathic pain.
2. To quantify changes in body perception.

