To achieve these aims, we will compare the effects of 3 different experimental conditions of neuro-visual stimulation on different pain and body perception measures (see below): Condition 1 - SCS ON and visual illumination via virtual reality of the body part where patients perceive paresthesia due to SCS (congruent neuro-visual stimulation); Condition 2 - SCS ON and visual illumination of a another sector of the visual field without paresthesia (incongruent neuro-visual stimulation); Condition 3 – SCS OFF and illumination of the congruent body part (baseline condition). We predict stronger effects in Condition 1, properly combining SCS and virtual reality stimulation. The comparison between condition 1 and 3 will measure the effect of SCS, while controlling for visual stimulation; the comparison between condition 1 and condition 2 will measure the additional benefit induced by multisensory stimulation in virtual reality. Primary outcomes of the treatment will be pain reduction, as quantified by means of subjective (visual analogue scales and questionnaires), functional (scales and assessments) and physiological measures (changes in heart rate variability) measures. Secondary outcomes will be changes in body perception, as assessed by questionnaires and behavioral tasks.

Significance of problem

Chronic pain is a major public health problem with implications for high health care costs, lost productivity and an estimated financial burden of \$500 billion.^{1,2} It leads to deterioration in overall health of individual suffering from pain.³ Epidural SCS is an FDA approved therapy for patients with refractory neuropathic pain associated with failed back syndrome (FBS) and complex regional pain syndrome type-1 (CRPS-1).^{4,5} Conventionally 40-60 Hz stimulation frequency is used for producing paresthesias in the affected body region ('coverage'). Initially paresthesias were thought to be critical for pain control (Gate control theory).⁶ However pain control can also be achieved with the non-paresthesia producing kilohertz frequency stimulation (1-10 KHz).⁷ Overall the mechanisms underlying SCS therapy are unclear.⁸ Investigations into the mechanisms underlying SCS efficacy are desirable to optimize outcomes and guide stimulation parameters (electrode contacts, amplitude, pulse width etc.) and integration with other technologies.

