Participants in this study will be adults who have already undergone implantation of SCS for the treatment of their pain conditions. The study involves no further treatment or intervention. Subjects will be approached for participation in this study during their routine postoperative clinical visit to the Center for Neuromodulation at the Ohio State University (OSU). Patients will be informed about the scope of this study and our aim of investigating basic brain functions in patients who have undergone SCS implantation. Patients will be informed about the study procedures, duration of participation. We wish to enroll 25 patients for this study. Although a power calculation for this type of observational study is not feasible, collecting data on 25 participants will allow us to investigate several patient populations and be able to capture heterogeneity reasonably well.

Inclusion Criteria

1. Age 18-and older at the time of enrollment
2. patients experiencing lower extremity pain e.g. neuropathy, CRPS type-1, neuropathic leg pain following FBS etc.^{4,25}
3. Patients who have implanted epidural SCS
4. The SCS implantation for at least three months prior to enrollment

5. Patients willing and able to provide informed consent

Exclusion criteria

1. Patients who are unable to effectively or efficiently communicate for example patients suffering from speech deficits (dysarthria, aphasia) or are non-English speaking.
2. Patients with history of prior cranial surgery, significant brain lesions for example intracranial tumors, strokes etc.
3. Evidence of untreated psychiatric disorders or drugs/alcohol abuse.
4. History of seizures

Equipment: (Figure 1.)

The VR system includes a head mounted display (Oculus Rift development Kit 2 (DK-2), Oculus VR, Irvine, CA). Patients will be comfortably seated while concurrently observing in first person perspective their own legs through the head-mounted display and captured on line via a camera. The RealiSM interface will allow for the integration of online recording of one's own body and virtual illumination of different parts of the visual field, depending on the different experimental conditions, as well as the presentation of the different outcomes measures. Device specifics are included with this submission.

Study Procedures (Figure 2)

Consent

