2. Oswestry Disability Index
3. Vital signs including pulse, blood pressure, respiratory rate, oxygen saturation, temperature and heart rate variability
4. Peri-personal space task
5. Embodiment questionnaire

Modulation of leg embodiment will be performed using a simple block design to study the SCS ON states with leg illumination paradigm in the following three conditions:

Condition 1: SCS ON and congruent leg illumination (neuro-visual)

Condition 2: SCS ON and incongruent leg illumination (SCS only)

Condition 3: SCS OFF and congruent leg illumination (vision only)

Condition 1 represents the target condition, combining SCS and virtual reality stimulation, i.e. neuro-visual stimulation. Condition 2 represents the effects of SCS stimulation only, while condition 3 represents the effects of visual stimulation only. The comparison between condition 1 and 3 will measure the effect of SCS, while controlling for visual stimulation; the comparison of condition 1 and condition 2 will measure the additional benefit induced by multisensory stimulation in virtual reality.

Overall each condition will be about 1 hour in duration. Taking into account the washout period (2 hours) between ON and OFF conditions, the whole experiment will be approximately 5 hours long, which will be distributed along a whole day visit, to avoid fatigue and between conditions carry-over effects. The patient will be encouraged to report the development of any discomfort or symptoms (dizziness, headache etc.) after and during each session. If a patient reports discomfort, the VR session will be immediately stopped.

Data management

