Data from source documents will be de-identified and stored in the CranialCloud™. CranialCloud™ is a “cloud-based” data capture platform developed by Neurotargeting, Inc. Through a rigorous risk assessment process, it has been approved by the OSUWMC Office of Information Technology and its Security Team, for the capture of clinical and/or research data inclusive of Protected Health Information (PHI) fields. A Business Authorization Agreement has been fully executed between the OSU Wexner Medical Center and Neurotargeting, Inc., regarding the clinical data management services, use and governance of CranialCloud™. All data is stored in a HIPAA compliant database system, is encrypted and is not visible to the administering team. The system automatically deidentifies all data entered and links it to an identification value. A separate database within the CranialCloud system is maintained with patient identifiers and the associated key.

Access to individual patient data within the database can be done through a secure login linked to the person's qualifications to access PHI. The list of persons authorized to view PHI (for example, treating

physicians, members of the surgical team, and specific research associates) will be determined by the study PIs. Once in the database, patient identifiers will be codified and not accessible for any queries outside of those listed above. Non-patient specific information can be analyzed, sorted or queried in response to specific statistical questions related to this protocol only by any investigator of the research team or other authorized person for this protocol. If subjects no longer wish to have their data tracked within the atlas, they can call the study team and have their name removed from any further data collection from the time of notification forward. All previously collected data will still be accessible and not expunged from the database.

Outcomes analysis

Analysis of the data obtained during different study conditions will be done offline, and will involve a wide variety of analytical and computation techniques to determine the best method/technique that can robustly detect the statistical differences.

Outcome measures

Analgesic effects

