We will assess the analgesic effects of neuro-visual stimulation using 1) subjective pain perception (pain rating) (Huskisson 1974), 2) functional impact (Oswestry Disability Index)²⁶ 3) objective physiological heart changes (Heart rate variability, HRV)²⁷ measured by Visimobile monitoring system as described below.

Pain rating

Subjective pain perception will be measured by pain ratings on a 10cm visual continuous analog scale (VAS). Patients will be asked to rate their pain, ranging from "no pain" (bottom part of the scale) to "the worst imaginable pain" (upper part of the scale) (Huskisson 1974).

Functional impact

Oswestry Disability Index is a commonly used validated scale to quantify disability associated with back pain²⁶. This scale measures the impact of back pain in ten different domains of life with 0 signifying no disability and 100 implying maximum disability.

Vital signs

The vital signs (pulse, blood pressure, respiratory rate, oxygen saturation, temperature) will be recorded using non-invasive monitoring with Visimobile monitoring system.

Heart rate variability (HRV)

HRV will be used as an objective physiological measure of analgesia, as low a HRV is associated with chronic pain and increase in HRV have been repetitively associated to pharmacologically-induced analgesia^{27,28}. ECG signals will be acquired online during the whole duration of the treatment and Inter-beat intervals will be calculated as the time between two successive R spikes. For each subject and each condition, we will calculate the square root of the mean squared differences of successive beats intervals (RMSSD), which estimates the short-term components of HRV and is commonly used over short recording periods²⁹.

Body perception

We will use validated questionnaires from EPFL in order to investigate induced changes in leg perception and ownership. In particular, we will assess: 1) feeling of ownership towards the leg shown in the virtual reality set-up (leg ownership); 2) tactile sensations felt on the virtual legs, depending on the different conditions of SCS and visual stimulation. Patients will be asked to indicate how much they agreed with each item using a 7-point colored vertical Likert scale ranging from 0 (complete disagreement, the bottom extreme, red point) to +6 (complete agreement, the top extreme, green point).

Peri-personal space

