The peripersonal space task will be used as an implicit measure of changes in body perception. We will use a dynamic visuo-tactile interaction task, implemented by means of the RealiSM technology, which measures the strength of multisensory integration within the space surrounding the leg. The rationale of the approach is that tactile stimuli on one's own body more effectively interact with external (visual) stimuli, when these are presented within the peripersonal space. Thus, the strength of multisensory interaction close to a part of the body can be considered on a measure of how much that body part is perceived as one's own^{30,31}. Subjects will sit on a chair and wear the virtual reality headset through which they will be able to see their own legs. A virtual ball will be showed as approaching the participant's legs. Along with the visual stimulus, participants will receive a tactile stimulation on their leg, delivered by means of a tactile stimulator at different temporal delays from the virtual stimulus appearance. This way, tactile stimulation will be associated with visual stimulation, at a different distance from the body. Trials with tactile stimulation only, with no virtual objects, will be also administered as a baseline condition. Participants will be asked to respond by button press as quickly as possible to the tactile stimulus. RT to tactile simulation when the virtual stimulus is perceived at a different distance will be compared with RT to tactile stimulation only in order to measure visuo-tactile interaction and its modulation as a function of the spatial location of the visual stimulus.

Compensation

Patients will be compensated for participating \$100 each visit for their participation in this study.

Ethics

None of the OSU investigators involved this study have any financial or academic conflicts of interest that influence their participation in this study. Patients will be carefully selected and all study procedures and protocols precisely in line with the final active protocol as approved by the OSU Biomedical IRB. Protected Health Information (PHI) of participants will be captured into the secure and password protected REDCap database but the final data set will be de-identified for statistical analysis and manuscript preparation.

Milestones

1. Clinical study – 24 months
2. Data analysis – 6 month
3. Report preparation – 3 month
4. Journal submission and publication – 3 months

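### The Outcomes analysis sentence lets the technique be chosen by how well it detects differences in the trial's own data, which inflates false positives and the effect if that technique supplies the headline result

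*Protocol*

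**What the plan says.** The protocol's only general description of the analysis method is in Outcomes analysis. It reads "Analysis of the data obtained during different study conditions will be done offline", and goes on to say that this analysis "will involve a wide variety of analytical and computation techniques to determine the best method/technique that can robustly detect the statistical differences". No hold-out sample or separate data set for choosing the technique is mentioned.

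Other sections fix parts of the analysis:

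- **Direction.** Specific Aims and predictions: "We predict stronger effects in Condition 1, properly combining SCS and virtual reality stimulation".
- **Contrasts.** The same section and VR session (Figure 2) name condition 1 v 3 and condition 1 v 2. Of the latter: "the comparison of condition 1 and condition 2 will measure the additional benefit induced by multisensory stimulation in virtual reality".
- **Heart rate variability.** One summary measure, RMSSD, per patient and condition.
- **Peripersonal space.** "RT to tactile simulation when the virtual stimulus is perceived at a different distance will be compared with RT to tactile stimulation only".

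The Population section gives the size: "We wish to enroll 25 patients for this study". The Abstract says the proof-of-concept "will form the basis for future NIH funding application".

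**The concern.** A technique judged by its success in detecting differences, on the same data from which the differences are then reported, is chosen on its result. A test selected that way no longer has its nominal error rate, and the estimate that goes with it tends to be too large when there is a true effect.

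This is not a complaint that detail has been left to a statistical analysis plan. The protocol states a rule for choosing the technique, and the rule is what is at fault. If an analysis plan fixes one test in advance, this sentence conflicts with it and still has to be rewritten.

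At stake is the comparison that the study predicts will favour condition 1, and the effect size carried from it into a funding application.

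**Working it through.** **What limits the rule.** The contrasts, RMSSD and the reaction-time comparison say what is compared and on which measure. None of them says how a technique is chosen, so none limits the selection sentence.

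**No figure to reproduce.** The protocol gives no alpha, power, effect size, SD or list of techniques. Everything below except n = 25 and the within-patient comparison is an assumption.

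**False positives.** For one outcome and one contrast with no true effect, the rate when the best of k techniques is kept is P(min(p1, ..., pk) < 0.05). Assumed: two-sided 5%; VAS mean 5.5, between-patient SD 1.5, within-condition SD 0.8, 1.2 or 2.0, clipped to 0–10; 20,000 trials of 25 patients per SD.

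| Technique(s) | Rate over the three SDs |
|---|---|
| Paired t alone | 4.9% |
| Wilcoxon alone | 4.7–4.8% |
| Sign test alone | 4.2–4.5% |
| Three-condition mixed model alone | 4.9–5.0% |
| Best of t, Wilcoxon | 5.7% |
| Best of t, Wilcoxon, sign | 7.3–7.6% |
| Those three plus mixed model | 8.0–8.3% |
| t after dropping differences beyond 2 SD, alone | 10.0–10.2% |
| Percent change alone | 5.5–8.0% |
| t, Wilcoxon, sign plus outlier-dropping t | 11.9–12.0% |
| t, Wilcoxon, sign plus percent change | 9.4–12.7% |
| t, Wilcoxon, sign plus both | 13.3–16.0% |

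Repeat runs on 25 paired differences gave 4.9–5.3% for t, 5.6–6.0% for t or Wilcoxon, 7.5–7.8% with the sign test added, and 11.6–12.1% with outlier dropping added. A different candidate set (t, Wilcoxon, sign, baseline-adjusted) gave 7.9–8.0% with normal data. With log-normal data it gave 9.1–9.2%, where the baseline-adjusted test alone ran at 5.5–6.3%.

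**Effect estimate.** Paired differences N(δ, 1), n = 25, 10,000 trials. The estimate reported is the one belonging to the lowest p among mean/t, Hodges-Lehmann/Wilcoxon and median/sign, then with the outlier-dropped mean added.

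| True δ (SD of differences) | Fixed t | Best of three | Plus outlier dropping |
|---|---|---|---|
| 0 | 0.003 | 0.003 | 0.003 |
| 0.2 | 0.198 | 0.210 | 0.221 |
| 0.4 | 0.399 | 0.409 | 0.429 |

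- Best of three at 0.2: (0.210 − 0.198)/0.198 = 6.1%.
- Best of three at 0.4: (0.409 − 0.399)/0.399 = 2.5%; against the true 0.4, 0.009/0.4 = 2.3%.
- With outlier dropping: 0.023/0.198 = 11.6% and 0.030/0.399 = 7.5%.
- At δ = 0 the signed estimate is not biased. Only its mean absolute size rises, from 0.159 to 0.196 (0.213 with outlier dropping).

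**Scale.** The 95% half-width for a fixed paired t test is t(0.975, 24)/√25 = 0.413 SD. The bias among valid tests, 0.010 to 0.012 SD, is about 1/41 to 1/34 of that.

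**The case against.** The best case for the plan is that the sentence is loose wording in a small study. It does not say that p-values choose the technique or that only the winner is reported, and *robustly* may mean stable across methods. The Approach section calls the study a pilot, no treatment decision hangs on a significance threshold, and the choice of test commonly belongs in the analysis plan.

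Much of this stands, and it limits what may be inferred:

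- **Selective reporting.** A reader might infer that the protocol commits to reporting only the winning technique. It does not say so, and the harm is conditional on that technique supplying the headline result.
- **Missing test and alpha.** These can properly sit in an analysis plan and carry no weight here.
- **Large inflation.** A reader might apply 1 − 0.95^k, giving 22.6% for five techniques and 40.1% for ten. That assumes independent results, whereas the techniques would be run on the same patients' data. Reporting the largest of four estimates gives 0.364 for a true 0.30 (about 21% too high), but the protocol describes no such rule.
- **A single primary outcome and contrast.** A reader might infer that the cure must reduce the study to one of each. The several primary pain measures and two contrasts raise a separate multiplicity question.

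What does not stand is that the sentence is harmless. It ends in finding a best technique, and best is tied to detecting differences. Pilot status lowers the consequence without removing the dependence on the result.

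**Conclusion.** The concern holds in conditional form. On its natural reading, the sentence makes the choice of technique depend on the result, and nothing else in the protocol limits it. If the chosen technique supplies the headline result, error rate and effect size are both inflated.

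For one outcome and one contrast with 25 pairs at an assumed two-sided 5%, the inflation is modest when every candidate is valid alone: about 6 to 8% false positives, and an estimate about 2 to 6% too high for true effects of 0.2 to 0.4 SD. It becomes material, about 12% or more, only with variants that are liberal alone. The protocol neither names nor excludes such variants, so those higher figures show a possible range and should not set the severity. The point should be fixed because the faulty wording is explicit and cheap to replace; confidence in the size is medium at most.

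**What to change.** Replace the sentence in Outcomes analysis with wording such as:

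> *For each primary pain measure and each planned contrast (condition 1 v 2 and condition 1 v 3), one analysis method is named before the condition data are examined. Any other technique is an exploratory or sensitivity analysis, is reported whatever its result, and does not replace the named analysis.*

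The named method could be, for example, a paired comparison reported as a mean difference with 95% confidence interval. The sponsor may prefer another method, provided that exactly one is named per measure and contrast: even a t test and a mixed model kept side by side gave 5.8–5.9% in the simulation. If an analysis plan already names the methods, the protocol sentence should point to it.

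The cost is one paragraph, with no new patients or data, and less analytic flexibility. At a true effect of 0.4 SD, the best of t, Wilcoxon and sign rejects in 53% of simulated trials against 48% for the fixed t test, but it does so with 7.4% false positives against 5.0%.

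Whether to reduce to a single primary outcome and contrast is not part of this change.
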